COMIRB Protocol

COLORADO MULTIPLE INSTITUTIONAL REVIEW BOARD
[name] [contact] [contact]

Protocol Version 3, 07/09/2015

Project Title: Aspiration in Acute Respiratory Failure Survivors

Principle Investigator: [name] MD

I. Hypothesis and Specific Aims

We hypothesize that the BSE assessment of swallowing certain consistencies will provide the most accurate diagnosis of aspiration.

A. Specific Aim #1: To develop a BSE-based non-invasive clinical prediction rule (CPR) that will accurately and efficiently diagnose aspiration in ARF survivors.

B. Specific Aim #2: To identify abnormalities in laryngeal structure and swallowing physiology that are associated with aspiration in ARF survivors.

Study Design: Prospective cohort study of patients with acute respiratory failure who require mechanical ventilation for more than 48 hours.

Inclusion Criteria:

1. Admission to an ICU.
2. Mechanical ventilation with an endotracheal tube for greater than 48 hours.

Exclusion Criteria:

1. Age < 18 years
2. Contraindication to enteral nutrition administration.
3. Pre-existing or acute primary central or peripheral neuromuscular disorder
4. Pre-existing history of dysphagia or aspiration.
5. Pre-existing head and neck cancer or surgery.
6. Presence of a tracheostomy.
7. Coagulopathy resulting in uncontrolled nasal or pharyngeal bleeding.
8. Unable to participate due to altered mental status
9. Extubated for greater than 72 hours.
10. Inability to obtain informed consent from patient or an appropriate surrogate.
11. Pregnancy
12. Imprisoned at the time of admission, anytime during the hospitalization, or anytime during the follow up period

First, a SLP will perform a comprehensive BSE on each ARF survivor.

Subsequently a second blinded SLP/investigator will perform the FEES to determine whether aspiration is truly present. The FEES examination will also identify abnormalities associated with aspiration.

For Aim #1: Primary Outcome Variable: Aspiration (PAS score of ≥ 6) on the FEES with any of the five feedings. A PAS score of ≥ 6 includes patients with both silent and non-silent aspiration.

Statistical analysis: Recursive partitioning or Classification and Regress Tree (CART) analysis creates a tree that asks a series of yes/no questions, taking the user down different branches depending on the answers. At the end of each branch will be an estimated probability of outcome.

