The BSE may not accurately diagnose aspiration in ARF survivors. By combining specific components of the BSE, clinical prediction rules (CPRs) have been developed for patients with head and neck cancer or cerebrovascular accidents.^{16-18;31;62-70} These disease-specific CPRs may not accurately detect aspiration in ARF survivors for the following reasons. 1) The proposed mechanisms responsible for aspiration in ARF survivors increase the likelihood of silent aspiration that would not be routinely detected on a BSE.^{9;59-61} 2) Decreased saliva production after radiation alters swallowing function and has been included in head and cancer specific CPRs.^{12-14;20;66;71} This criterion would most likely not contribute to aspiration in ARF survivors. 3) Some aspiration CPRs were developed using only patients referred for formal swallowing evaluations; creating both a selection bias and limiting generalizability of the results.^{69;70;72} 4) Due to their diminished respiratory reserve, the consequences of aspiration are greater in ARF survivors.⁷³ Therefore CPRs might need to be more sensitive for the detection of aspiration. 5) Certain CPRs were developed without comparison to a gold standard test of aspiration such as a VFSS or FEES.^{69;70;72} 6) The 3 ounce water swallow test (3-WST) is a sensitive initial screening test in hospitalized patients. However, it is unclear whether the 3-WST applies to ARF survivors, or what BSE components could be combined with the 3-WST to confirm aspiration.⁷⁴⁻⁷⁶

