Part 3: Three Ounce Water Swallow Test (3-WST): During the standardized 3-WST, patients receive three ounces of water and are instructed to drink the entire amount, via cup or straw, completely and without interruption (the cup can be held to the patient's mouth by the SLP).^{74;76;109} The 3-WST will be scored as pass/fail. Criteria for failure of the 3-WST are: the inability to drink the entire amount, coughing or choking up to 1 minute after completion, or the presence of a wet-hoarse vocal quality.

At this point the SLP will document their diet recommendations, and whether further invasive testing (MBSS or FEES) is indicated.

Subsequently, the SLP can perform additional testing including specific maneuvers. The results of these additional tests will be recorded in the CRF. The SLP will then document their diet recommendations that include the knowledge gained from the additional testing. Again the SLP will document whether further invasive testing (MBSS or FEES) is indicated.

Based on these recommendations, the patient will be allowed to advance their diet prior to the performance of the FEES, if indicated.

The coordinator should make sure that the BSE CRF is completely filled out before the SLP who completed the test leaves the ICU.

The BSE form for consistency testing is attached as Appendix.

3. FEES examination: The SLP will review the subject's medical record and become knowledgeable with the patient's medical history. The FEES examination will be performed by a second SLP who is blinded to the results of the BSE. The FEES should be performed within approximately 4 hours of the BSE.

Similar to the BSE, the patient should be seated with the head of the bed as elevated as possible. At the discretion of the SLP/investigator, Afrin and Lidocaine spray can be administered into the nasal passage before the laryngoscope is inserted. The use of these medications will be noted in the case report form.

Part 1: First the SLP will perform and videotape the examination of the upper airway. Velar closure, base of the tongue retraction, laryngeal elevation, right and left vocal cord/arytenoid mobility, right and left pharyngeal wall medialization, epiglottic retroflexion, granuloma formation, and upper airway edema will be assessed.

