Laryngeal sensation will be assessed by observing the laryngeal adductor reflex (LAR) or a patient response to a light touch/poke to the aerepiglottic folds bilaterally with the tip of the laryngoscope, and scored dichotomously.

Part 2: Standardized consistency testing: The SLP will then administer five standard consistencies in two trials of each consistency with different amounts.¹⁰⁶

Boluses will be administered from lowest to highest aspiration risk: 1) $\frac{1}{2}$ tsp, then 1 tsp ice chips, 2) 1 tsp of nectar thick liquids, then 3 tsp of nectar thick liquids, 3) a 2 ounce patient controlled administration of nectar thick liquids, 4) 1 tsp of pureed solids (applesauce), then 10 mls of pureed solids (applesauce), 5) 5 mls of thin liquids (water or milk), 15 mls of thin liquids (water or milk), and a 2 ounce patient controlled administration of thin liquids and 6) $\frac{1}{4}$ of a graham cracker.¹⁰⁷ The patient will be instructed to chew the graham cracker before swallowing. In order to limit the complexity and duration of our consistency testing, honey-thick liquids will be excluded from the protocol.

Table 3: PAS scoring system

Scale	Enters airway?	Relationship to vocal folds	Ejected from airway?	Effort made to eject?
1	No	--	--	--
2	Yes	Above	Yes	--
3	Yes	Above	No	--
4	Yes	Contacting	Yes	--
5	Yes	Contacting	No	--
6	Yes	Below	Yes	--
7	Yes	Below	No	Yes
8	Yes	Below	No	No

After the swallow, the laryngoscope will be advanced to closely view the patient's airway. The SLP will wait for 10 seconds following the completion of each individual trial before recording the results for that consistency. If necessary, patients will be allowed to drink water between consistency tests to clear any remaining residue from their upper airway.

The entire FEES will be video recorded. The SLP will score each of the trials using the PAS score (Table 3).

In addition for each of the trials of the consistencies, the SLP will record the following two physiological measures:

- 1) Swallowing onset time: The time from first bolus visualization until swallow onset.
- 2) Incomplete bolus clearance: leaving residue in the pharynx or laryngeal vestibule after a swallow.

Using the video recordings, the quantification of the swallowing onset time and incomplete bolus clearance will be determined by a single observer.

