Part 3: Three Ounce Water Swallow Test (3-WST): During the standardized 3-WST, patients receive three ounces of water and are instructed to drink the entire amount, via cup or straw, completely and without interruption (the cup can be held to the patient's mouth by the SLP).^{74;76;109} The 3-WST will be scored based on the PAS scoring system.

The results of the different components of the FEES assessment will be made available to the treating team if requested.

The coordinator should make sure that the FEES CRF is completely filled out before the SLP who completed the test leaves the ICU. See Appendix for FEES evaluation form.

4. Outcome Assessments

All patients will be followed for the subsequent outcome assessments.

Date of ICU discharge

ICU length of stay

Date of hospital discharge

Hospital length of stay

Discharge location

Reintubation since enrollment

If yes, date of reintubation

Died during ICU stay

Died during hospital stay

Surgical feeding tube placed?

5. Statistical analysis for Aim #1: Recursive partitioning or Classification and Regress Tree (CART)

analysis creates a tree that asks a series of yes/no questions, taking the user down different branches depending on the answers. At the end of each branch will be an estimated probability of outcome.

Statistically, recursive partitioning is a non-parametric approach to regression, in this case logistic regression.

We will predict a class Y (aspiration vs. non-aspiration) based on the predictor variables, X₁...X_n which can be either categorical or continuous. The main characteristic of this method is that predictor variables are “split” and partitions are created so that observations with the same response variable are grouped together.

After the first split, further splits of variables will occur based on the groups which are made from the prior split separately. The goal is to group observations with the same response class minimizing

misclassification. Some of the benefits of using recursive partitioning are that the splits are data driven, predictor variables can be used multiple times, and interactions will be included without having to decide which interactions are important. An algorithm (or tree) is obtained that splits the predictor variables until each person has been classified as with aspiration or non-aspiration in a terminal node. Pruning of the tree will take place by determining a value of the change in misclassification rate which is deemed too small to

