include the next branches on the trees. By splitting the data up into ten sets and choosing one set each time, ten-fold cross-validation will estimate the misclassification rate for the tree. The chosen set will be sent through a tree developed from randomly choosing nine of the sets. The misclassification for this set will be calculated, and performed 10 times until each set has been sent through a tree. An average rate of misclassification is developed to determine how well the tree based on all the data will perform on new data.

Sample Size Calculation and Feasibility: Based on our 18 month data from the two medical centers, there were a total of 1087 patients who remained on mechanical ventilation for at least 48 hours and lived to be discharged to home or self-care. For recursive partitioning, there are no specific sample size calculations. However, in a simulated data analysis, a sample size of 200 yielded an area under the curve (AUC) of .75 for the resultant tree algorithm. To be conservative, we will enroll a total of 225 patients. Based on our estimated number of ARF survivors, we will need to obtain consent from only 20.6% of them to achieve our enrollment goal. This is a very conservative estimate for obtaining informed consent for research on swallowing function.

Additional Considerations: Our primary analysis will develop a CPR for the combined outcome of silent and non-silent aspiration. We will also develop a CPR for silent aspiration alone defined as a PAS score =8, and a CPR for non-silent aspiration alone defined as a PAS score of 6-7. For each of the five different consistencies, the accuracy of the BSE assessment for aspiration will also be compared to the presence of aspiration of the FEES examination (PAS ≥6). Sensitivity, specificity, positive and negative predicted values will be determined with 95% confidence intervals for each point estimate. Based on a sample size of 225 patients, the width of each 95% confidence interval point estimate will be 2-4%.

Statistical analysis for Aim #2: For each outcome and independent variable, a univariate logistic regression model will be developed. If the Wald test for an individual variable in the logistic regression model is significant at the p <0.10 level, the variable will be included in a multivariable logistic regression model. ROC curves will be constructed to determine how well the regression models correctly predict

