cracker) Bolus given: YES NO	Not Determined If penetration (2-5): 
 
 Before Swallow	During Swallow	
 
 After Swallow	
 
 If aspiration (6-8) 
 
 Before Swallow	During Swallow	
 
 After Swallow	
 
	Before Swallow	During Swallow	After Swallow		Before Swallow	During Swallow	After Swallow		Not Done	Not Done Residue location: Circular all that apply 
 
 BOT	valleculae	Lateral channels	
 
 piriforms	Laryngeal vestibule		
 
 Response to residue: 
 
 Spontaneous clearing	None	
 
	BOT	valleculae	Lateral channels	piriforms	Laryngeal vestibule		Spontaneous clearing	None
Before Swallow	During Swallow																		
After Swallow																			
Before Swallow	During Swallow																		
After Swallow																			
BOT	valleculae	Lateral channels																	
piriforms	Laryngeal vestibule																		
Spontaneous clearing	None																		

3 oz Water Swallow Test:

Patient is given a cup with 3 oz water. He is asked to drink the entire amount, slowly and steadily, but without stopping. He can drink from the cup or a straw and the SLP can hold the cup or straw

Was the 3 oz water test performed? YES NO

If yes complete the following table.

Did the patient stop 1+ times	Did the patient finish the entire amount	Cough/Choking	Change in Voice	Wet Breath Sounds	No signs of aspiration
 Yes  No					

RESULTS of 3 oz water test? PASS FAIL

Pass= drinks the entire amount without stopping (use your judgment), and without coughing, choking during or immediately after completion.

Fail = does not finish the total amount, stops 1+ times (for more than a few seconds), or has overt signs of aspiration immediately after swallowing

Reference List

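### As worded, the Aim 1 outcome leaves out the FEES 3-ounce water test, so aspiration seen only on that test would be labelled non-aspiration

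*Combined protocol and SAP*

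**What the plan says.** The opening summary, under For Aim #1: Primary Outcome Variable, sets the outcome as "Aspiration (PAS score of ≥ 6) on the FEES with any of the five feedings". The word feedings is not defined.

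The FEES procedure (Study Procedures, section 3) has two separate swallowing parts:

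- **Part 2** opens with "The SLP will then administer five standard consistencies in two trials of each consistency with different amounts". The consistencies are ice chips, nectar-thick liquid, puree, thin liquid and graham cracker. The largest single amount is 2 ounces, taken under patient control.
- **Part 3** is the 3-ounce water test, drunk without a break. The text says "The 3-WST will be scored based on the PAS scoring system".

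The FEES form in the Appendix gives every Part 2 bolus a PAS field. For the 3-ounce test it prints only clinical signs and "RESULTS of 3 oz water test? PASS FAIL".

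On the bedside side, the 3-ounce test is Part 3 of the BSE (section 2, Bedside Evaluation): "The 3-WST will be scored as pass/fail". The Background treats it as a candidate building block and says it is unclear "what BSE components could be combined with the 3-WST to confirm aspiration".

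**The concern.** The FEES is the reference standard that is meant to settle whether a patient really aspirates. If the label uses Part 2 only, a patient with PAS 5 or lower on every Part 2 bolus and PAS 6 to 8 on the 3-ounce test is a non-aspirator for Aim 1, although aspiration was seen on the reference examination.

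The affected patients are not a random subset. They aspirate only on the largest uninterrupted water swallow, which is the challenge that the bedside 3-ounce test also poses. When such a patient fails at the bedside, a correct result is booked as a false positive. What is at stake is the label that the tree is trained on, and any estimate of the bedside 3-ounce test's accuracy against that label.

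**Working it through.** **Which swallows count.** The plan states no figure on this point, so there is none to reproduce. Three places have to be read together:

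1. The outcome refers to five feedings.
2. The only set of five in the FEES procedure is the Part 2 consistencies. Additional Considerations, under the Aim 1 analysis, again speaks of five consistencies.
3. The 3-ounce test has its own part and its own scoring sentence, and no section adds its PAS score to the outcome.

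The plain reading therefore leaves the test out.

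**Illustration of size.** Inputs:

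- N = 225 (Sample Size Calculation and Feasibility).
- Aspiration on the five consistencies: 50%, the rate in the 26-patient pilot (Preliminary Data, item 5). Non-aspirators as labelled: 225 × 0.50 = 112.5, taken as 113.
- Assumed: 5 to 10% of the 113 aspirate only on the FEES 3-ounce test. k = 0.05 × 113 ≈ 6, or 0.10 × 113 ≈ 11.
- Assumed: bedside 3-ounce specificity of 70% under the narrow label. True negatives: 0.70 × 113 ≈ 79. False positives: 113 − 79 = 34.
- Varied: f, the share of the k patients who fail the bedside 3-ounce test.

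Under the narrow label, specificity = 79/113 = 69.9%. Once the k patients are relabelled as aspirators, those who passed at the bedside leave the true negatives:

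specificity = [79 − (1 − f)k] / (113 − k)

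| f | k = 6 | k = 11 |
|---|---|---|
| 100% | 79/107 = 73.8% | 79/102 = 77.5% |
| 50% | 76/107 = 71.0% | 73.5/102 = 72.1% |
| 30% | 74.8/107 = 69.9% | 71.3/102 = 69.9% |
| 0% | 73/107 = 68.2% | 68/102 = 66.7% |

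The break-even lies at f = 30% because that is the false-positive rate under the narrow label (1 − 0.70). Above it, the narrow label understates specificity. Below it, the narrow label overstates specificity, and patients who pass at the bedside become false negatives once relabelled.

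Positive predictive value moves one way only. The number of bedside failures is fixed, and f × k of them change from false to true positives. If all fail, that is 6 or 11 of the 34 apparent false positives; if half fail, 3 or 5.5 of 34.

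**Against sampling error.** The 95% half-width around 70% with 113 patients is 1.96 × √(0.70 × 0.30 / 113) = 0.084, or about ±8 points.

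**The case against.** The strongest reply is that the wording is ambiguous rather than wrong. Feedings is undefined, water is a thin liquid, and thin liquid is one of the five consistencies, so a team could count the 3-ounce test under it. That reading is possible, but no section adopts it. If two analysts can derive different primary outcomes from the same text, the definition needs the same repair.

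A second reply concerns size. An affected patient must get through every Part 2 bolus, including 2 ounces of thin liquid, and then aspirate on 3 ounces; the documents give no rate for this. The Background also expects much aspiration in these patients to be silent and missed at the bedside, so it would be wrong to assume that all of them fail there. Even the largest shift in the table is within the sampling error. These points stand and limit the claim about size. They do not change the label.

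Three stronger inferences are tempting and not supported:

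- **That the analysis text sets a wider definition.** A reader might take "presence of aspiration of the FEES examination (PAS ≥6", under Additional Considerations, to mean the whole examination and so to contradict the outcome wording. The sentence begins by restricting itself to each of the five consistencies, so it shows no such contrast.
- **That rinse water should be scored too.** In Part 2, "patients will be allowed to drink water between consistency tests to clear any remaining residue from their upper airway", but only where needed and in no stated volume. Counting it would give some patients extra chances to be positive, and aspirated material could be residue from the previous bolus.
- **That the tree is steered away from the bedside 3-ounce test.** The predictors are not listed. The test's entry into the tree is a fair inference from the Background and the BSE procedure, and Potential Scientific Problems implies that its accuracy will be assessed. No calculation shows what the tree would do.

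**Conclusion.** The point holds as a defect in the outcome definition. On its most natural reading, the Aim 1 outcome omits a FEES swallow that the protocol says is PAS-scored, and a patient who aspirates only on that swallow is labelled a non-aspirator. A bedside 3-ounce failure in that patient then counts as a false positive.

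The size is unknown. With 113 non-aspirators, 5 to 10% of them affected and a reported specificity of 70%, the understatement runs from about 0 points if 30% of the affected patients fail at the bedside, through 1 to 2 points if half fail, to about 4 to 7.5 points if all fail. Below 30% the direction reverses. The affected share, the 70% and the bedside failure rate are all assumptions. The documents support neither a claim that the bias is large nor a claim that specificity is always understated.

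**What to change.** - Define the Aim 1 primary outcome as PAS ≥ 6 on any protocol FEES trial, meaning any Part 2 bolus or the FEES 3-ounce water test. State which trials feed the separate silent and non-silent aspiration rules.
- Add a PAS field for the 3-ounce test to the FEES form, or score that test from the video, since the whole FEES is recorded. This also brings the form into line with the Part 3 text.
- Classify patients who did not have the FEES 3-ounce test on their Part 2 trials, and report how many there are.
- Report the five-consistencies-only definition as a sensitivity analysis. It also shows how many labels change, which the documents cannot tell us now.

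The cost is one sentence of outcome wording, one derived variable, and a small form change or some video scoring. No new procedure is needed. The aspiration rate may come out slightly higher than the 50% seen in the pilot.

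### The plan promises a probability of aspiration at the end of each branch but cross-validates only the misclassification rate, so branch probabilities are neither checked nor corrected and are likely to be too extreme

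*Combined protocol and SAP*

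**What the plan says.** The Aim #1 analysis is given in the opening summary and again under Statistical analysis for Aim #1. Both places describe the end product of the tree: "At the end of each branch will be an estimated probability of outcome". The fuller section adds that the algorithm "splits the predictor variables until each person has been classified as with aspiration or non-aspiration in a terminal node", so a terminal node carries a class label as well as a probability. Neither place says how the probability is calculated.

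On growing the tree, the plan notes as an advantage that "the splits are data driven, predictor variables can be used multiple times". Pruning rests on "determining a value of the change in misclassification rate which is deemed too small to" justify further branches; no value is given. No minimum node size and no list of candidate predictors appears.

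On validation, "ten-fold cross-validation will estimate the misclassification rate for the tree", and the purpose is stated as follows: "An average rate of misclassification is developed to determine how well the tree based on all the data will perform on new data". The 95% confidence intervals promised under Additional Considerations are for sensitivity, specificity and predictive values of the bedside evaluation by consistency, not for branches of the tree.

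On size, the basis is that "a sample size of 200 yielded an area under the curve (AUC) of .75 for the resultant tree algorithm", followed by "To be conservative, we will enroll a total of 225 patients". All 225 are used for development.

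**The concern.** A classification rule and a risk estimate need different checks. Misclassification depends only on which label a branch carries. With the label set by majority, it does not change when the published probability moves from 20% to 35%. A held-out AUC would not settle the matter either, because it depends only on how patients are ranked.

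The direction of the likely error is known. The search keeps splits because the resulting groups look unusually low or high in the patients at hand. A proportion computed in those same patients inherits the chance part of that contrast. New patients falling in a low branch will on average aspirate more often than the branch states, and those in a high branch less often.

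The plan's background says that speech-language pathologists would use such a rule for feeding recommendations, and Significance names harm on both sides: aspiration, and oral feeding delayed without need. Probabilities that are too low at one end and too high at the other would mislead in both directions.

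**Working it through.** **1. The plan's own figure.** The one performance figure behind Aim #1 is the AUC of 0.75 at n = 200. It cannot be reproduced: the simulation's number of predictors, signal, prevalence, node size and pruning are not given, nor whether the AUC is apparent or held-out. The documents give no figure for error in branch probabilities.

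**2. What misclassification can see.** Take 100 new patients in a branch labelled non-aspiration, of whom 35 aspirate.
- Published probability 20%: 35 misclassified. Published probability 35%: also 35 misclassified.
- Brier score, mean of (outcome − probability)². At 20%: 0.35 × 0.80² + 0.65 × 0.20² = 0.224 + 0.026 = 0.250. At 35%: 0.35 × 0.65² + 0.65 × 0.35² = 0.2275.

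The planned measure cannot separate the two; a probability-based measure can. A cross-validated error above the apparent error would hint at optimism overall, but would not say in which branch or by how much.

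**3. How wide the search could be.** The bedside case report form lists 13 physical-examination items and 11 boluses. Two boluses carry 4 aspiration signs and 4 oral-phase findings; nine carry 5 and 4. That gives 13 + 2 × 8 + 9 × 9 = 110 items, before the 3-ounce water test and baseline variables. The plan does not say which are candidates.

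**4. Size, by simulation.** From the documents: n = 225; prevalence 44% (Significance), with 50% (pilot of 26 patients, Preliminary Data) as an alternative. Everything else is assumed: yes/no signs, Gini splits, node proportions as probabilities. Each branch's shown proportion was compared with its true risk in 6,000 independent patients. One setting, 400 replicates: 60 signs each present in 40% of patients, correlation 0.1, three informative with odds ratio 6 (best achievable AUC about 0.82). Entries are points.

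| Minimum node | Pruning | All branches shown below 50%: true − shown | Highest branch: shown − true | Tree AUC, new patients |
|---|---|---|---|---|
| 7 | none | 12.1 | 25.3 | 0.74 |
| 7 | fixed 1% | 10.0 | 13.7 | 0.75 |
| 7 | minimum cross-validated error | 5.8 | 8.9 | 0.72 |
| 7 | one-standard-error | 4.2 | 6.8 | 0.71 |
| 20 | none | 6.0 | 11.0 | 0.78 |
| 20 | fixed 1% | 5.8 | 5.8 | 0.77 |
| 20 | minimum cross-validated error | 4.2 | 5.0 | 0.73 |
| 20 | one-standard-error | 3.1 | 4.2 | 0.71 |

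At 50% prevalence with minimum node 7, the low-branch column reads 14.5, 12.6, 6.3 and 4.3.

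Over a wider set of assumptions with real signal (13 to 120 signs; 3 to 6 informative, odds ratios 2.5 to 6; prevalence 35 to 50%; minimum node 7 or 20), low branches combined understated risk by 6 to 16 points without pruning, 6 to 15 at fixed 1%, 3 to 6 at minimum cross-validated error and 3 to 4 under the one-standard-error rule. A separate simulation with 25 to 110 signs, node 7 or 20 and pruning at 1% or 3% gave about 4 to 17. Together: roughly 3 to 17. The direction was the same in every setting.

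**5. How much is selection by observed value.** With three pre-fixed splits and no search, branches picked because they showed 30% or less still understated risk: 19.5% shown against 23.1% true, 20.2% against 22.5%, 24.1% against 28.7%, or 3.6, 2.3 and 4.6 points. That part is ordinary regression to the mean.

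**6. Whether recalibration helps.** In the simulation that gave 4 to 17 points, an intercept and slope fitted to out-of-fold logits, with extreme values clipped, brought group-average probabilities to within about 5 points of the truth.

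**The case against.** The strongest reply is that the plan is about classification. Aim #1 is to diagnose aspiration, the stated aim of splitting is low misclassification, and the sentence on branch probabilities sits in a general description of the method. For a yes/no rule, ten-fold cross-validation of misclassification is a relevant check, with each held-out set run through a tree built on the other nine. This stands as far as it goes: a reader might infer that the tree is never validated, and that is not so. What lacks a check is the branch probability, which the plan states as an output in two places.

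A reader might also take the raw node proportion to be the plan's stated method. It is the usual default, but the plan is silent, so the bias is conditional on it.

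A reader might fix on one size of bias, or put all of it down to the tree search. The documents support neither. Node size, pruning, number of signs and signal all move the result, and some of the gap in branches picked by an observed cut-off would arise without any search.

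Finally, no section ties a feeding decision to a probability threshold, so a count of patients managed differently cannot be derived from the documents.

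**Conclusion.** The point holds in this form: the plan promises branch probabilities, validates only the yes/no call, and provides no calibration check, optimism correction or interval for those probabilities. If they are node proportions, low-risk branches will tend to understate aspiration and high-risk branches to overstate it. The understatement over low-risk branches combined is roughly 3 to 17 points under the assumed inputs. It is about 3 to 5 in the tabulated setting with cross-validation-based pruning and a minimum node of 20, and above 10 with small nodes and little pruning. Nothing in the plan secures the favourable case. The direction is firm; the size is not, because it rests on assumptions about pruning, node size, sign count and signal that the documents do not supply. The change is worth making but is not fatal to Aim #1.

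**What to change.** Keep the tree and the ten folds, and add one SAP paragraph:

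- State in advance the minimum node size, the pruning value or rule, and how the branch probability is computed. Listing the candidate signs at the same time would make the search explicit.
- Repeat growing and pruning inside each fold, and save each held-out patient's predicted probability. Bound or smooth these so that branches at 0% or 100% have finite logits, and state the rule.
- Fit a logistic calibration intercept and slope of outcome on the held-out logits.
- Publish recalibrated branch probabilities with 95% confidence intervals next to the raw ones.
- Report observed against predicted risk by band, the calibration slope and the Brier score, alongside the planned misclassification rate.

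No new data are needed. The cost is somewhat more analysis work and published probabilities that look less extreme. One limit should be stated: a single intercept and slope, estimated from ten fold-specific trees and applied to the final tree, corrects probabilities on average and does not guarantee each branch.
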